Microneurography Recording of multiunit postganglionic **muscle sympathetic nerve activity** (MSNA) will be made from the common peroneal nerve as it winds around the fibular head with the subject in the supine position with her thigh comfortably supported. This procedure requires us to first trace the course of the nerve using small electrical stimuli applied to the surface of the skin over the nerve. This allows the microneurographer to find and focus the recording electrode tip on a nerve fascicle associated with muscle sympathetic activity. The time required to focus the electrode on the nerve averages about 30 min and will not exceed 60 min. In optimal conditions the track of the nerve from superficial stimulation is accurate and the nerve remains in position during insertion. An uninsulated subcutaneous electrode will serve as the reference. Mechanoreceptor afferent activity can be recorded during light tapping on the muscle belly or passive muscle stretch. A suitable intrafascicular recording site for MSNA consists of regular bursts and synchronous with the cardiac cycle. The neural activity is amplified (2×10^4), filtered (0.5-5.0 kHz), rectified, and integrated. The amplified and filtered nerve signal is also led to an audio monitor and through a resistance capacitance circuit (time constant 100 ms). The integrated nerve signal is digitized at 400 Hz along with the ECG signal while respiratory and arterial pressure signals are also sampled at 400 Hz (MacLab 8s). Data for analysis is selected from periods of quiet breathing in which subjects were relaxed and not talking. Microneurography was approved under HIC # 8079, #0512000875 and HIC #1609018353

Cardiovascular variables. Recorded with a 16-channel computerized data-acquisition system at a sampling Speed of 400 Hz (ADI Instruments PowerLab 9, Castle Hill, Australia). Beat-to-beat DBP, SBP and pulse interval (PI) are determined using peak detection algorithms (44). Brachial artery BP and HR are measured with an automated sphygmomanometer (Colin Medical Instruments Corp, Komaki, Japan). Heart rate and pulse interval will be determined beat-to-beat from lead II of the ECG recording.

Cardiovagal baroreflex sensitivity, as we previously described (88), will be determined by slope of linear relationship between PI and SBP at rest, during Valsalva maneuver (67, 87), and during the modified Oxford technique (21, 23, 65, 66). **R&R:** At rest, baroreflex sequence requires three

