or more consecutive beat-to-beat increases in PI with simultaneous increase or decrease in SBP (7). Only those sequences with a correlation greater than 0.85 are included in the analysis. Average of individual slopes in each condition will be taken as a measure of resting cardiovagal BRS. Incidence of baroreflex sequences will be reported as sequences per 100 pulses to normalize for differences in HR among subjects and across experimental days (55). We recognize that this method for evaluating BRS has limitations (49), but it is a widely accepted method, is predictive of cardiovascular morbidity (58), and is an indicator of autonomic control (21). **Sympathetic baroreflex sensitivity** will be evaluated by determining slope of the linear relationship between MSNA and DBP at rest, during Valsalva maneuver and during the modified Oxford technique (23, 65, 66). **R&R:** MSNA can be distinguished from other sources of nerve activity by the following criteria: 1) presence of spontaneous pulse synchronous bursts; 2) increased activity during Valsalva; 3) muscle afferent activity with muscle stretch; 4) no change of activity during light stroking of skin or startling the subject with loud noises, indicating a lack of skin nerve activity. **Valsalva maneuver:** Subjects will perform Valsalva maneuver following deep inspiration: expiratory mouth pressure (measured with a pressure transducer; 40 mm Hg, 20 seconds) by blowing through a 1-inch diameter tube against an open glottis. **Cardiovagal baroreflex** is assessed during phase IV (overshoot phase) of the Valsalva maneuver, the phase occurring right after the release of the strain (67, 87). Consecutive SBP values during phase IV will be linearly regressed against corresponding PI from the SBP time point where PI begins to lengthen and continued to the point of maximal BP increase. **Lower body negative pressure** and **Forearm blood flow (FBF)**, as previously described by us (88).

Blood sampling. Blood sampling is done via 20-gauge catheter placed in an arm vein. Subjects will be in the posture they will assume for at least 30 min prior to sampling to ensure a steady state in plasma volume and constituents. Blood sampling is done from free-flowing blood. Approximately 60ml of blood (4 tablespoons) will be removed for analysis.

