Aim 1: Statistical analyses: Univariate statistics [mean (SD)] will be generated on all study variables first, which will determine the normality or the heteroscedacity of the data. Data will be analyzed using SPSS 21 statistical software that includes calculations to compensate for missing data, and Prism (GraphPad) curve fitting software where appropriate. **Data analysis.** The slopes of the linear regressions for PI-SBP (cardiovagal baroreflex gain), PI-LBNP (integrated baroreflex gain), resting MSNA, slopes for MSNA-DBP (sympathetic baroreflex gain during Oxford and Valsalva), will be compared between treatment conditions (GnRH antagonist vs. GnRH antagonist+T and between groups (Control vs AE-PCOS) using a 2-way repeated measures ANOVA with supplemental *post hoc* testing with Tukey's HSD test. **Sample size.** The desired statistical test is two-sided, and we assume an alpha level of =0.01 to account for multiple comparisons (37). In our laboratory, we observed effect sizes (SD) of PI-SBP intercept (with n=4) of 0.39 (0.16), our most stringent variable. A sample size of 15 women per group will allow us \geq 80% statistical power ($1-\beta > 0.9$) to test within group comparisons, and this same sample size will allow $[1-\beta]=0.80$ to distinguish any between-group differences from chance alone (29). Due to the technical challenges of performing microneurography on multiple occasions in obese women, we overestimate and account for a $\sim 20\%$ failure rate, so we will recruit 18 subjects per group. **R&R:** **1) GnRH antagonist suppression/hormone add-back** is the gold standard and most reliable method to control sex hormones in young women. **2) Microneurography** is the gold standard and most sensitive and reliable available measure for MSNA. **3) Lower body negative pressure** and the **Modified Oxford Technique** are the gold standards and most sensitive and reliable

available measures of autonomic function in humans. We will report our methods and findings in detail and **full transparency** to permit others to reproduce and extend our findings. **Sex as a biological variable:** Only women are included in these studies because AE-PCOS is a female-specific disorder.

Aim 2: Statistical analyses: We use ANOVA as described in Protocols 1. **Sample Size** is based on calculations in Aim 1, as the Aim 1 variables are the more stringent.

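### The resting baroreflex sequence rule, with its correlation filter, keeps only sequences in which PI and SBP both rise, which roughly halves the sequence count and costs precision

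*Combined protocol and SAP*

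**What the plan says.** Section V.3, Procedures, paragraph on cardiovagal baroreflex sensitivity, says that this quantity "will be determined by slope of linear relationship between PI and SBP at rest, during Valsalva maneuver" and during the modified Oxford test. For the resting measure it adds:

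- Eligibility: "At rest, baroreflex sequence requires three" "or more consecutive beat-to-beat increases in PI with simultaneous increase or decrease in SBP".
- Filter: "Only those sequences with a correlation greater than 0.85 are included in the analysis".
- Summary: "Average of individual slopes in each condition will be taken as a measure of resting cardiovagal BRS".
- Second reported quantity: "Incidence of baroreflex sequences will be reported as sequences per 100 pulses".

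No other sentence admits runs in which PI falls. The threshold is stated on a correlation; neither its absolute value nor its square is mentioned. Section V.12 (Aim 1) lists among the quantities to be compared between treatment conditions and between groups "The slopes of the linear regressions for PI-SBP (cardiovagal baroreflex gain), PI-LBNP (integrated baroreflex gain), resting MSNA". The plan also notes: "We recognize that this method for evaluating BRS has limitations (49), but it is a widely accepted method".

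**The concern.** A spontaneous baroreflex sequence is a run in which pulse interval follows pressure: both lengthen and rise, or both shorten and fall. The written rule fixes the direction of PI and leaves SBP free. It therefore names as eligible a discordant run (PI up, SBP down) and gives no place to a concordant one (both down). The filter in the next sentence conflicts with the first of these, because a discordant run cannot have a high positive correlation. The words allowing SBP to decrease can never produce an analysed sequence.

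At stake are the precision of resting cardiovagal BRS and the meaning of the reported incidence. Baroreflex sensitivity is named in Aims 1 and 3, and the expected-results text predicts PI-SBP changes under paced breathing at rest. Section V.12 also undertakes to report methods so that others can reproduce the work, and this rule does not describe a two-direction measure.

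**Working it through.** There is no stated figure to reproduce, since this is a measurement definition. The check has four steps.

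**1. Direction and sign.** If PI rises strictly over a run while SBP falls strictly, their covariance is negative, so r < 0. An assumed four-beat example (SBP 118, 120, 121, 123 mm Hg; PI 850, 872, 884, 905 ms, with order reversed as needed) gives:

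| PI | SBP | r | slope (ms/mm Hg) | eligible as written | kept at r > 0.85 |
|---|---|---|---|---|---|
| up | up | +0.9998 | +11.0 | yes | yes |
| up | down | −0.9998 | −11.0 | yes | never |
| down | down | +0.9998 | +11.0 | no | – |
| down | up | −0.9998 | −11.0 | no | – |

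Only the first row survives both sentences.

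**2. Count and precision.** Assume n concordant sequences, half up and half down, with similar slope scatter and roughly independent. The rule keeps n/2. The standard error of a woman's mean slope is multiplied by √(n ÷ (n/2)) = √2 ≈ 1.41.

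**3. Illustrative simulation.** This used 400,000 simulated beats, an assumed gain of 15 ms/mm Hg in both directions, and three assumed levels of PI noise. The comparison is between both-up plus both-down runs and the rule as written, each with signed r > 0.85:

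| Noise | Sequences per 100 beats, both directions | as written | ratio | Mean slope, both directions | as written |
|---|---|---|---|---|---|
| low | 11.91 | 5.94 | 0.50 | 18.66 | 18.67 |
| medium | 8.06 | 4.04 | 0.50 | 27.44 | 27.37 |
| high | 5.94 | 2.96 | 0.50 | 41.76 | 41.49 |

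With assumed unequal gains (15 up, 10 down), the mean slope moved from 16.97 to 17.23 (0.26/16.97 = +1.5%) at low noise and from 26.22 to 26.10 (−0.12/26.22 = −0.5%) at medium noise. The simulated means exceed the gain put in because runs are selected for agreement. Only the contrast between rules is informative.

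The paced-breathing rest in Section V.3 lasts seven minutes. At an assumed 60 to 80 beats/min that is 420 to 560 beats. Two-direction counts would be about 25 (420 × 5.94/100) to 67 (560 × 11.91/100) per woman. As written they would be about 12 (420 × 2.96/100) to 33 (560 × 5.94/100).

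**4. Carry-over to group comparisons.** Let k be the within-woman variance of the mean slope under the two-direction rule, divided by the between-woman variance. Halving the sequences multiplies the standard error of a group mean by √((1 + 2k)/(1 + k)). The documents give no k. Assumed values of 0.1, 0.5 and 1 give √(1.2/1.1) = 1.04, √(2/1.5) = 1.15 and √(3/2) = 1.22, all below 1.41.

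**The case against.** The strongest reply is that the filter already does the important work. A correlation above 0.85 plainly means signed r, so no discordant run reaches the averaged slope. That stands. It disposes of the stronger reading that a reader might infer, namely that discordant runs with negative slopes are averaged in and pull resting BRS toward zero. If a share f of kept runs were discordant with equal and opposite slopes, the mean would be multiplied by (1 − 2f), for example 0.60 at f = 20%. In the simulation above, a filter on |r| lowered the mean slope from 18.66 to 18.12, 27.44 to 22.81 and 41.76 to 27.06 (3%, 17% and 35%). All of this needs a filter on |r| or r-squared, which the documents do not state, and they give no discordant share. Nor would that bias come with a full halving of incidence: under |r| the counts were 6.03, 4.39 and 3.56 per 100 beats, or 51%, 54% and 60% of the two-direction counts.

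Three further replies have some force:

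- The same rule applies to both groups and all visits, so a lower count is not in itself a differential bias. This stands.
- A rising-only measure is not invalid in principle. The plan's own Valsalva slope uses only the stretch from the start of PI lengthening to peak pressure. This also stands, but there the restriction is stated deliberately for one phase of a manoeuvre. Here the wording suggests that two directions were meant.
- It is probably a drafting slip, and the cited method or the laboratory's software may already be correct. That is plausible but cannot be seen from the documents, and the written rule is what a reader would follow. The acknowledged limitations of the method are general and do not mention direction.

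**Conclusion.** The rule is wrong as written, with modest consequences. Taken together, the eligibility sentence and the filter analyse both-rising sequences only. If up and down runs are similar in number, and incidence is counted on the filtered sequences (the plan does not say), the reported incidence is about half the two-direction value. With similar slope scatter and roughly independent sequences, the within-woman standard error of resting cardiovagal BRS rises about 1.4-fold. The mean slope is little changed: within 1.5% in the simulation, whose gains and noise are assumptions. The loss in group comparisons is smaller, by an amount that the documents do not allow one to fix. The documents do not support a claim that the mean slope is biased toward zero.

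The point is confined to the resting sequence index. The modified Oxford slope and the Valsalva phase IV slope are defined separately in Section V.3 and do not use this rule.

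**What to change.** Replace the eligibility sentence in Section V.3 (Procedures) with a definition along these lines: a resting sequence is a run of three or more consecutive beats in which SBP and PI both increase or both decrease, with signed r > +0.85. Make clear whether the minimum of three counts beats or beat-to-beat changes, since the present text counts changes. State that up and down slopes are averaged together and that incidence per 100 pulses is counted on those same filtered sequences. Confirm that the software setting matches.

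The cost is one or two sentences and a check of one setting. No new data are needed: if the beat-to-beat recordings are kept, sequences already collected can be re-extracted under the clarified rule.

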Sympathetic baroreflex sensitivity assessment: modified Oxford technique (Aim 1). To assess baroreflex control of sympathetic outflow, HR, BP, MSNA and PI will be measured during arterial pressure changes induced by infusion of sodium nitroprusside (SNP, endothelium-independent vasodilator) and phenylephrine (PE, an α -receptor agonist) (20, 23, 42). After 10-minute baseline period, SNP (100 μ g bolus) will be given followed 1 minute later by PE-HCL (150 μ g). This protocol decreases BP~15 mm Hg below baseline levels and then increases BP~15 mm Hg above baseline levels over a short period of time (See bottom tracing, **Fig 9**). Infusions are sequential, repeated twice in each subject with at least 15 minutes between each cycle of infusions. **Fig 9** shows change in BP and increase in (integrated) MSNA that follows SNP infusion, and the decreased MSNA following PE infusion in a typical subject. Sympathetic baroreflex sensitivity is defined as the slope relating MSNA and DBP during the sequential infusions of SNP and PE (20). Cardiovagal baroreflex sensitivity is defined as the slope relating PI and SBP (20, 23, 42). The modified **modified Oxford technique** has been approved under HIC #0512000875. The PE and SNP will be infused by [name] (Emergency Medicine).

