Statistical analyses: Univariate statistics [mean (SD)] will be generated on all study variables first, which will determine the normality or the heteroscedacity of the data. Data will be analyzed using SPSS 21 statistical software, that includes calculations to compensate for missing data, and Prism (GraphPad) curve fitting software where appropriate. **Data analysis.** The slopes of the linear regressions for PI-SBP (cardiovagal baroreflex gain), PI-LBNP (integrated baroreflex gain), resting MSNA, slopes for MSNA-DBP (sympathetic baroreflex gain during Oxford and Valsalva), will be compared between treatment conditions (GnRH antagonist vs. GnRH antagonist+T and between groups (Control vs AE-PCOS) using a 2-way repeated measures ANOVA with supplemental *post hoc* testing with Tukey's HSD test. **Sample size.** The desired statistical test is two-sided, and we assume an alpha level of =0.01 to account for multiple comparisons (37). In our laboratory, we observed effect sizes (SD) of PI-SBP intercept (with n=4) of 0.39 (0.16), our most stringent variable. A sample size of 15 women per group will allow us $\geq 80\%$ statistical power ($1-\beta > 0.9$) to test within group comparisons, and this same sample size will allow $[1-\beta]=0.80$ to distinguish any between-group differences from chance alone (29). Due to the technical challenges of performing microneurography on multiple occasions in obese women, we overestimate and account for a $\sim 20\%$ failure rate, so we will recruit 18 subjects per group. **R&R:** **1) GnRH antagonist suppression/hormone add-back** is the gold standard and most reliable method to control sex hormones in young women. **2) Microneurography** is the gold standard and most sensitive and reliable available measure for MSNA. **3) Lower body negative pressure** and the **Modified Oxford Technique** are the gold standards and most sensitive and reliable available measures of autonomic function in humans. We will report our methods and findings in detail and **full transparency** to permit others to reproduce and extend our findings. **Sex as a biological variable:** Only women are included in these studies because AE-PCOS is a female-specific disorder.

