Characterization of the RAS during LBNP in humans (Aim 2). We will use the protocol described in **Fig 7** with the hormone intervention described in **Fig 8**. Before beginning the protocols, during 7° HDT, at 0 (supine rest) and in the final minute of each level of LBNP we will draw blood to determine $S_{[ALD]}$, $S_{[ACE]}$, $S_{[ANG]}$, $P_{[Renin]}$, PRA, $P_{[ANG\ II]}$, $P_{[NE]}$, $P_{(38)}$, electrolytes, Cr and Osm. Urine samples will be collected just prior and after baroreflex/RAS LBNP protocol for electrolytes.

Statistical analyses: We use ANOVA as described in Protocols 1. **Sample Size** is based on calculations in Aim 1, as the Aim 1 variables are the more stringent.

Expected results, interpretation of data, limitations and anticipated problems: Based on our hypothesis, **we expect** that women with AE-PCOS will have greater RAS hormonal responses to LBNP, reflecting greater RAS activation. **We expect** that testosterone suppression will reduce PRA, $S_{[ALD]}$, $S_{[ANG\ II]}$, PRA and $P_{[Renin]}$ response to LBNP, suggesting lower RAS activation in both Control and AE-PCOS. **We expect** that increasing $P_{[Tfree]}$ and FAI will increase RAS hormone response to LBNP, reflecting greater RAS activation responses to LBNP in AE-PCOS. Since the methods to be used are in place in our laboratory, we don't anticipate any problems in performing the studies in this Aim.

Expected results, interpretation of data, limitations and anticipated problems: **We expect** AE-PCOS women will have greater resting MSNA compared to Controls. **We anticipate** that slopes for MSNA-DBP will be greater in AE-PCOS, indicating increased sympathetic BRS compared to Control. **We expect** that testosterone suppression will decrease slopes for MSNA-DBP in AE-PCOS, and testosterone administration will increase slopes for MSNA-DBP in both Control and AE-PCOS. In contrast, **we expect** reduced slopes of PI-SBP with modified Oxford and paced breathing, indicating decreased sympathetic and cardiovagal BRS in AE-PCOS women; **we expect** a steeper PI-SBP slope with androgen suppression, and a steeper PI-SBP slope with modified Oxford, as well as paced breathing and Valsalva in both groups. Since all methods to be used are in place in our laboratory, we don't anticipate any problems in performing the studies in this Aim.

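### The Valsalva rule, read literally, makes SBP the response, which conflicts with the PI-SBP gain the rest of the plan uses; the sentence should name PI as response and SBP as predictor

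*Combined protocol and SAP*

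**What the plan says.** All references are to the combined protocol and SAP.

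- **Section V.3, Procedures, Valsalva maneuver:** "Consecutive SBP values during phase IV will be linearly regressed against corresponding PI", from the point where PI begins to lengthen to the point of maximal BP increase. No slope unit is given.
- **Section V.3, Procedures, Cardiovagal baroreflex sensitivity:** the measure is the "slope of linear relationship between PI and SBP at rest, during Valsalva maneuver" and during the modified Oxford technique. One definition covers all three settings.
- **Section V.3, modified Oxford technique (Aim 1):** "Cardiovagal baroreflex sensitivity is defined as the slope relating PI and SBP".
- **Section V.3, Statistical analyses, repeated in Section V.12:** "The slopes of the linear regressions for PI-SBP (cardiovagal baroreflex gain") are compared between treatment conditions and between groups by repeated measures ANOVA.
- **Expected results in Section V.3, repeated in Section V.12:** the plan expects "reduced slopes of PI-SBP with modified Oxford and paced breathing, indicating decreased sympathetic and cardiovagal BRS in AE-PCOS women", and also "a steeper PI-SBP slope with modified Oxford, as well as paced breathing and Valsalva in both groups".

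The Valsalva sentence is the only one that gives a regression direction for any cardiovagal slope. The others name the two variables without saying which is the response.

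**The concern.** To regress Y against X normally makes Y the response. An analyst who follows the Valsalva sentence would fit SBP as a function of PI and obtain a slope in mm Hg/ms. A baroreflex gain is response per unit stimulus, so it should be the change in PI per mm Hg of SBP. The expected-results text treats it that way, since it equates a reduced PI-SBP slope with reduced sensitivity.

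The two slopes differ in units and usually in direction, and one cannot be recovered by inverting the other unless the points lie exactly on a line. The Procedures list Valsalva as a source of cardiovagal sensitivity, and the expected results state a direction for it. What is at stake is therefore the sign and scale of the androgen and group effects on this measure. Two analysts could also take the same beats and report results that point in different ways.

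**Working it through.** **Inputs.** The regression direction comes from the Valsalva sentence, and the intended meaning from the other four places quoted. The documents give no cardiovagal gain in ms/mm Hg, no SBP spread in phase IV, no PI scatter and no beat count. All such values below are assumptions. The plan has no figure on this point to reproduce.

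**Step 1: the two slopes.** Let g be the slope of PI on SBP and r the correlation.

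- PI on SBP: g = r × sd(PI)/sd(SBP), in ms/mm Hg.
- SBP on PI: r × sd(SBP)/sd(PI) = r²/g, in mm Hg/ms.
- Reciprocal of the second: g/r², which overstates g by the factor 1/r².

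That factor is 1/0.9025 = 1.11 at r = 0.95, 1/0.81 = 1.23 at r = 0.90 and 1/0.7225 = 1.38 at r = 0.85. It changes with the fit of each woman and session.

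**Step 2: direction.** Let s be the SD of SBP and e the residual SD of PI. Then r² = g²s²/(g²s² + e²), and the literal slope is g·s²/(g²s² + e²). Its derivative in g has the sign of e² − g²s², so with s and e fixed it falls as g rises only when g²s² > e², that is, when r² > 0.5.

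With assumed s = 8 mm Hg:

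| e (ms) | literal slope as g rises (mm Hg/ms) |
|---|---|
| 30 | 0.111 (g = 2), 0.128 (g = 5), 0.033 (g = 30) |
| 120 | 0.009 (g = 2), 0.033 (g = 15, r² = 0.50), 0.027 (g = 30) |

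The inverse relation therefore holds for good fits and not for noisy ones. The plan's floor, "Only those sequences with a correlation greater than 0.85 are included in the analysis", implies r² above 0.72, but it is set for resting sequences. None is stated for Valsalva.

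**Step 3: illustration.** Assume gain doubles from 8 to 16 ms/mm Hg, with r = 0.85 at gain 8.

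- At gain 8: 0.7225/8 = 0.0903 mm Hg/ms.
- At gain 16 with r held at 0.85: 0.7225/16 = 0.0452, a fall of one half.
- At gain 16 with s and e held: g²s²/e² goes from 0.7225/0.2775 = 2.604 to 4 × 2.604 = 10.41. So r² = 10.41/11.41 = 0.912, and the slope is 0.912/16 = 0.057, a fall of about 37%.

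**Step 4: simulation.** 5,000 phase IV runs were simulated per gain, each with 10 beats, SBP rising from 110 to 140 mm Hg with 1 mm Hg noise, and PI residual SD 40 ms (all assumed).

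| True gain (ms/mm Hg) | PI on SBP (ms/mm Hg) | SBP on PI, as written (mm Hg/ms) |
|---|---|---|
| 5 | 5.04 | 0.130 |
| 10 | 10.00 | 0.089 |
| 20 | 20.04 | 0.048 |

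Regressing PI on SBP recovers the gain. The literal rule runs the other way.

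**The case against.** The strongest reply is that this is loose phrasing and not a reversed analysis. The verb is often used casually for any two-variable fit. The Procedures place Valsalva under the same PI-SBP slope as rest and Oxford. The naming also supports PI as response: the companion slopes are PI-LBNP and MSNA-DBP, and since LBNP is set by the experimenter, the response comes first. All of this stands. It shows what was probably intended, but the one operational sentence still says the opposite.

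A reader might infer more than the documents support:

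- **That the plan has definitely adopted a reversed regression.** The intended orientation is only implied elsewhere, and the documents do not settle whether the sentence is deliberate.
- **That a stronger reflex always gives a smaller literal slope, or that doubling the gain halves it.** The first needs r² above 0.5 with scatter and spread fixed. The second also needs r to stay constant while gain doubles.
- **That Valsalva results would be tested against Oxford or resting results and found to contradict them.** The stated comparisons are between treatment conditions and between groups. No test across maneuvers is planned.
- **That gains will be inflated by inversion.** The plan never proposes to invert the slope. The 1/r² factor shows only that inversion would not repair the problem.

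It is also fair that Valsalva is one of several overlapping sensitivity measures, that the baroreflex testing paragraph labels it sympathetic, and that a slope near 0.05 beside Oxford gains in ms/mm Hg would probably be noticed. These points limit the harm but do not remove the inconsistency.

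**Conclusion.** Wrong as written. The Valsalva sentence conflicts with the gain used in the rest of the plan. Followed literally, it yields r²/gain in mm Hg/ms, a quantity that generally moves opposite to the gain when the fit is good and that mixes gain with noise when it is not. Valsalva comparisons between conditions and groups could then be read in the wrong direction against the expected results.

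The algebra needs no assumption beyond least squares. The direction depends on r² above 0.5 with scatter and spread fixed. The illustrated fall of 37% to 50% rests on assumed gains and an assumed r. The finding is confined to the Valsalva cardiovagal slope; sample size and data collection are not affected.

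**What to change.** Amend the Valsalva paragraph in Section V.3, Procedures, to say that the PI of each beat (ms, response) is regressed on the corresponding SBP (mm Hg, predictor) over the phase IV segment already described, with the slope reported in ms/mm Hg. State the same orientation for the resting and modified Oxford cardiovagal gains, where no response variable is named. It would also help to say whether any minimum correlation applies to Valsalva, since the existing floor covers resting sequences only.

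The cost is one sentence, plus a clause in the two related definitions. If any Valsalva slopes have already been computed the other way round, the regression can be re-run on the stored beat data. No new measurement is needed.
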